1.1 PROTOCOL ABSTRACT AND SUMMARY

1.2 Protocol Abstract

Estrogen receptor negative (ER(-)), progesterone receptor-negative (PR(-)) breast cancer represents approximately 25 - 30% of all breast cancers. Unlike estrogen receptor-positive (ER(+)) breast cancer, patients with ER(-)/PR(-) disease are not candidates for current anti-hormonal strategies. The biology of ER(-) disease is poorly understood and with the exception of trastuzumab for Her2/neu-positive tumors, targeted therapy options are limited. Genome-wide expression analysis has revealed a subset of ER(-)/PR(-) breast cancers that share a gene expression profile with hormone receptor-positive tumors¹. Among these shared genes is the androgen receptor (AR). In-vitro studies of androgen blockade demonstrated a reduction in growth of ER(-)/PR(-)/AR(+) breast cancer cells. Clinical investigation of androgen blockade in breast cancer patients is therefore a rational therapeutic strategy.

The primary objective of this Phase II study is to evaluate the efficacy of bicalutamide (CasodexTM, Astrazeneca), a well-tolerated anti-androgen used in prostate cancer, in women with ER(-)/PR(-)/AR(+) metastatic breast cancer. Efficacy will be measured by the response rate (RR), including those patients with a demonstrated complete response (CR), partial response (PR), or stable disease (SD) after 6 months from the first day of therapy. Secondary objectives include progression-free survival (PFS), safety and correlative studies. Correlative studies, including peripheral blood hormone levels and selected immunohistochemical markers, will further characterize the biology of this novel subtype of breast cancer. This is an important study for the field of breast cancer research because bicalutamide may allow a greater number of patients with breast cancer the option of treatment with hormonal therapy instead of, or in addition to, chemotherapy.

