1.3 Protocol Summary

This is a multicenter, open-label, phase II study to evaluate the antitumor activity and safety of bicalutamide administered orally daily to patients with ER(-)/PR(-)/AR(+) metastatic breast cancer. Patients with measurable or non-measurable, metastatic breast cancer are eligible. Prior neo-adjuvant or adjuvant chemotherapy is permitted. There is no restriction on prior chemotherapy or hormonal therapy. Prior therapy with trastuzumab is allowed but may not be administered while on study.

Patients with metastatic, ER(-), PR(-) breast cancer may consent to androgen receptor testing while on breast cancer-directed treatment. If they are found to have AR(+) disease, they will be considered potentially eligible for treatment on study. At the time their treating physician determines they require a change in therapy, they may consent to participate in this study if they meet remaining eligibility criteria.

Eligible patients who have consented to trial participation will receive bicalutamide at a dose of 150mg PO daily. Up to two dose reductions of 50mg each will be allowed for grade 3 or 4 toxicity as specified by the protocol. The primary aim of the study is to evaluate the efficacy of

IRB#: 07-022A(13)

bicalutamide after 6 months of therapy. The study is a phase II design with a planned enrollment of 28 patients. If 4 or more patients demonstrate a response (defined as either a CR, PR or SD) after 6 months of therapy, bicalutamide will be considered a feasible and potentially promising therapy. Patients with progression of disease will be withdrawn from the study. Treatment may continue after 6 months in the absence of progression of disease or unacceptable toxicity.

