2.1 OBJECTIVES AND SCIENTIFIC AIMS

2.2 Primary Objective

The primary objective of this study is to:

• Evaluate the efficacy of treatment with bicalutamide at 6 months for patients with ER(-) /PR(-)/AR(+) metastatic breast cancer in terms of response (CR, PR) and SD.

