4.1 OVERVIEW OF STUDY DESIGN/INTERVENTION

4.2 Design

This is a multicenter, open-label, one-stage, phase II study to evaluate the antitumor activity and safety of bicalutamide administered orally daily to patients with ER(-)/PR(-)/AR(+) metastatic breast cancer. Patients with non-measurable or measurable, metastatic breast cancer are eligible. Prior neo-adjuvant or adjuvant chemotherapy is permitted. Prior therapy with trastuzumab is necessary for patients with Her-2/neu positive disease (3+ IHC or FISH > 2.0). There is no limitation on prior treatment with chemotherapy or hormonal therapies.

After signing the protocol consent form for androgen receptor testing, the patient's tumor will be evaluated for androgen receptor status using a commercially available immunohistochemical analysis. Androgen receptor testing may occur on primary breast tumor or tissue from biopsy of a metastatic site. Participating centers may send unstained slides to MSKCC for ER, PR and AR testing. Participating sites may instead choose to perform androgen receptor testing themselves however, estrogen receptor, progesterone receptor and androgen receptor status will be centrally confirmed at Memorial Sloan-Kettering Cancer Center by the Department of Pathology for tumors which test ER(-)/PR(-)/AR(+) locally. If this patient meets the remaining eligibility criteria for study participation, they may later consent to treatment on study. Patients with ER(-)/PR(-)/AR(+) breast cancer on local testing may begin bicalutamide if otherwise eligible while confirmation of receptor status at MSKCC takes place. If the patient's tumor is AR(-) at MSKCC, or if either estrogen or progesterone receptors are positive at MSKCC, the patient may continue on treatment with bicalutamide if the tumor tested ER(-), PR(-), AR(+) locally.

IRB#: 07-022A(13)

The primary aim of the study is to evaluate the efficacy of bicalutamide in terms of response (CR+PR) and SD at 6 months. The study has a projected enrollment of 28 patients. If 4 or more patients demonstrate a response (defined as a CR, PR or SD by RECIST criteria) after 6 months of treatment, bicalutamide will be considered a feasible and promising therapy.

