4.3 Intervention

Patients will receive bicalutamide at a dose of 150mg PO daily. Patients will be seen monthly for an assessment by a care provider familiar with the protocol. Clinical assessment and serum studies will be performed per protocol (See Time and Events Schedule, Section 10). Patients may be seen before their scheduled monthly follow-up if they are experiencing any adverse effects or symptoms that may be consistent with progression of disease. Patients will undergo a radiologic extent of disease evaluation (EOD) every 3 months. An EOD may be performed earlier than a 3 month interval if progression of disease is suspected. Response will be evaluated using RECIST criteria as complete response (CR), partial response (PR), stable disease (SD) or progressive disease (PD).

If a patient experiences unacceptable toxicity at the initial dose level, up to two dose reductions of 50mg each will be permitted. Dose reduction of bicalutamide from the initial dose of 150mg PO daily to100mg PO daily will occur for an individual patient if that patient experiences unacceptable toxicity. A second dose reduction of 50mg is acceptable. Toxicities will be graded using the NCI Common Terminology Criteria for Adverse Events (CTCAE) Version 3. Treatment may be delayed no more than 2 weeks to allow recovery from acute toxicity. In the event of a treatment delay exceeding 2 weeks, the patient will be withdrawn from the study.

[figure not shown]
A patient will be withdrawn from the study in the following situations:

- For an unacceptable toxicity, defined as a Grade 3 or 4 non-hematologic toxicity after 2 (50 mg) dose reductions (see Section 11.2.5); or
- For unacceptable toxicity that fails to resolve after a maximum treatment delay of 2 weeks; or
- Progression of disease

Treatment with bicalutamide will continue until one or more of the criteria for withdrawal from study are met. After 6 months of treatment, patients will be considered responders if they achieve a CR, PR or SD by RECIST criteria. At the investigator's discretion, and in the absence of disease progression by RECIST criteria, treatment with bicalutamide may continue beyond 6 months. Study drug is provided by AstraZeneca.

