4.4 Correlative Studies

As a secondary objective, correlative studies will be performed to further elucidate the biology of this potentially novel subtype of ER(-)/PR(-)/AR(+) (ER(-) Class A) breast cancer and to measure the effect of androgen blockade on peripheral hormonal levels.

IRB#: 07-022A(13)

In patients with prostate cancer, the use of bicalutamide leads to increased testosterone and estrogen levels. Little data is available for women treated with androgen blockade, but changes in hormonal levels are anticipated. A serum hormone panel will be drawn at baseline, after one month and at the end of study. This serum hormonal panel will include: estradiol, total and free testosterone, and sex-hormone binding globulin.

Doane and colleagues describe a panel of IHC markers that identifies ER(-) class A breast cancers. A combination of ER, PR, SPDEF and ALCAM was estimated to predict ER(-)/PR(-) samples as ER(-) Class A with a sensitivity approaching 100% (95% CI 69 -100%) and a specificity of 94% (95% CI 79-99%)¹. Other genes that are overexpressed in ER(-) Class A will also be evaluated for their protein expression with IHC including Her2/neu and FGFR4. Her2/neu has been previously shown to stabilize AR protein levels and optimize binding of AR to promoters of androgen-regulated genes in prostate cancer cells¹⁴. FGFR4 is overexpressed in ER(-) Class A tumors, and previous research has demonstrated molecular 'cross-talk' between FGFR4 and Her2/neu leading to activation of the mTOR translational pathway and subsequent cyclin D1 activation¹⁵. This convergence of data suggests that further investigation into the role of FGFR4, Her2/neu and AR in ER(-) Class A breast cancers is warranted.

The ER(-) Class A subtype was noted by Doane and colleagues to be distinct from the 'basal subtype' previously identified by Perou and colleagues¹⁶. The basal subtype generally corresponds to a proportion of ER(-) breast cancers. Cytokeratins 5/6 and 17 are expressed in the basal subtype but not in the ER(-) Class A subtype. Correlative studies of CK 5/6 and 17 will be performed to further explore these previously noted differences in expression patterns between the ER(-) Class A and a basal subtypes.

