10.0 EVALUATION DURING TREATMENT/INTERVENTION

Day 0 and every 4 weeks (+/- 5 days), the following clinical and laboratory assessments must be done prior to continuation of treatment with bicalutamide:

- History and physical examination, including:
 - Vital signs
 - ECOG performance status
 - o Weight
 - Concomitant medications
- Laboratory assessments, including: (screening labs can be used as Day 0 labs)
 - CBC with differential and platelet count
 - Comprehensive metabolic panel (Na, K, Cl, CO2, BUN, Creatinine, Ca, Glucose, Total Protein, Albumin, Alkaline Phosphatase, Total Bilirubin, AST and ALT)
- Adverse Event Evaluation (toxicity assessment using the NCI CTC version 3)
- Blood for correlative study of hormonal levels including estradiol, total testosterone, free testosterone, and sex-hormone binding globulin will be performed at baseline, after Cycle #1 and at the end of study. (See further description below)

Every 12 weeks (+/- two weeks), tumor assessments will be performed. Patients with measurable disease will be evaluated for complete response (CR), partial response (PR), stable disease (SD) or progressive disease (PD) using RECIST criteria, using the same modality of imaging performed at baseline. Patients with non-measurable disease will be evaluated for either stable disease or progressive disease. Responders and stable disease patients will continue on study unless they develop unacceptable toxicity. Progressive disease or unacceptable toxicity (after a maximum of two dose reductions) will be the criteria for treatment failure and discontinuation from the study.

Response assessment will include:

- Radiologic scans of disease sites (e.g. CT scan of chest, abdomen and pelvis and PET or bone scan if there are bone lesions identified on pre-study bone imaging)
- Measurement of all target lesions that are followed by physical examination
- Patients achieving a CR or PR must have confirmation of response at least 4 weeks following the initial response determination.
- End-of-Study (EOS) Evaluation: At the time patients are removed from study, laboratory and clinical evaluations to assess adverse events (AEs) will be performed. Serum hormone panel including estradiol, free and total testosterone and serum hormone binding globulin will be collected. Radiologic studies for antitumor response will be repeated if they have not been performed within the previous 28 days.

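### Does leaving 6 months undefined in weeks, with no deciding scan named, undermine the primary endpoint?

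*Combined protocol and SAP*

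**What the plan says.** The time point is worded in several ways. The abstract (Section 1.2) counts "stable disease (SD) after 6 months from the first day of therapy". The primary objective (Section 2.2) is to "Evaluate the efficacy of treatment with bicalutamide at 6 months", and Section 4.2 refers to "response (CR+PR) and SD at 6 months". Section 4.3 says "After 6 months of treatment, patients will be considered responders if they achieve a CR, PR or SD by RECIST criteria". Section 14.0 counts 6 months from the first treatment day and divides by all patients treated. For the separate measurable-disease rate it uses a greater-than sign before the 6 months. Section 12.1 names the endpoint without a time point.

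For scans, Section 10.0 says "Every 12 weeks (+/- two weeks), tumor assessments will be performed". Section 4.3 gives the interval as 3 months, Section 9.2 and the Time and Events Schedule as 3 cycles of 4 weeks, and Section 12.1 as 12 weeks. The same interchange appears elsewhere. Section 4.3 says "Patients will be seen monthly for an assessment by a care provider familiar with the protocol" where Section 10.0 has visits every 4 weeks. Section 4.4 says "A serum hormone panel will be drawn at baseline, after one month and at the end of study" where Section 10.0 times the middle sample after cycle 1.

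The design in Section 14.0 is single-stage with 28 patients. It calls the drug worth further study at 4 or more successes, and it separates true rates of 5% and 20% with type I error 5% and type II error 16%.

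**The concern.** Stable disease counts as success, so a patient succeeds simply by not having visibly progressed when the deciding scan is taken. The date of that scan therefore feeds directly into the success rate. The verdict can turn on one patient, 4 against 3 of 28.

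No section converts 6 months into weeks, names the second scan as decisive, or says how a scan taken slightly early is scored. On calendar months, nearly every second scan timed from day 0 would come before the time point, by up to about four weeks. A strict reading of the greater-than sign in Section 14.0 could send an analyst to the third scan near week 36. Two analysts could then classify the same patient differently, and the stated error rates hold only if 5% and 20% are the rates at the assessment actually scored.

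**Working it through.** **1. The stated design.** Inputs from Section 14.0: n = 28, success at 4 or more, rates 5% and 20%. With X binomial:

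- P(X ≥ 4 | 0.05) = 1 − (0.2378 + 0.3505 + 0.2490 + 0.1136) = 0.049.
- P(X ≤ 3 | 0.20) = 0.0019 + 0.0135 + 0.0457 + 0.0990 = 0.160, so power is 0.840.

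Both stated errors reproduce.

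**2. Which week is 6 months?** The scan interval is 3 months = 3 cycles = 3 × 4 = 12 weeks. Two intervals give 6 months = 6 cycles = 24 weeks, the second scheduled scan. A window of ±2 weeks counted from day 0 gives weeks 22 to 26. Section 10.0 does not state that anchor; if each window runs from the previous scan, the range is weeks 20 to 28. Calendar months would give 365.25 / 2 / 7 = 26.09 weeks.

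**3. Effect of the window.** The documents give no failure curve, so I assume exponential time to failure. If p is the rate at T weeks, the rate at week w is p^(w/T). For scans spread evenly from week a to week b, the mean rate is

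T / (b − a) × [p^(a/T) − p^(b/T)] / (−ln p).

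For T = 24 and weeks 22 to 26:

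- Null: 24/4 × (0.0642 − 0.0390) / 2.996 = 0.0505.
- Target: 24/4 × (0.2287 − 0.1749) / 1.609 = 0.2006.

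Putting such mean rates into the 4-of-28 rule:

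| Reading and scan pattern | Null rate | Type I error | Target rate | Power |
|---|---|---|---|---|
| 24 weeks, scans over weeks 22–26 | 0.0505 | 5.1% | 0.2006 | 84% |
| 24 weeks, scans over weeks 20–28 | 0.0521 | 5.6% | 0.2024 | 85% |
| 24 weeks, every scan at week 22 | 0.0642 | 10.2% | 0.2287 | 91% |
| 26.09 weeks, scans over weeks 22–26 | 0.0641 | 10.1% | 0.2281 | 91% |
| 26.09 weeks, every scan at week 22 | 0.0800 | 18.2% | 0.2574 | 95% |
| 26.09 weeks, decided at week 36 | 0.0160 | 0.1% | 0.1085 | 36% |

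Replacing the exponential by Weibull shapes 0.7 to 1.5 (rate p^((w/T)^k)) moves the first row's type I error only between 5.0% and 5.2%. For calendar months over weeks 22 to 26 the range is 8.2% to 14.0%.

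**4. Would a one-sided window help?** Suppose the deciding scan could be taken only in weeks 24 to 26. With 5% and 20% as week-24 rates, the mean rates become 12 × (0.0500 − 0.0390) / 2.996 = 0.044 and 12 × (0.2000 − 0.1749) / 1.609 = 0.187, giving type I error 3.4% and power 80%. Patients scanned only in weeks 22–23 would also score as failures. As separate illustrations, starting from the 20% rate and 84% power:

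- Losing 5% of true successes: 0.20 × 0.95 = 0.19, power 81%.
- Losing 10%: 0.20 × 0.90 = 0.18, power 77%.
- Losing half, if scan timing did not adapt at all: 0.20 × 0.50 = 0.10, power 31%. This is an outer bound.

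**The case for a change.** The strongest case for a change is that the equation of 6 months with 24 weeks is inferred and never stated, and that the greater-than sign in Section 14.0 sits badly with a week-24 scan. Even on the 24-week reading, a scan at week 22 precedes the time point. Under the exponential assumption, 1 − 0.0500/0.0642 = 22% of week-22 successes at the 5% rate would have failed by week 24, and 1 − 0.2000/0.2287 = 13% at the 20% rate. CR and PR need confirmation at least 4 weeks later, but SD has no such rule, so silent progression after an early scan can go unseen.

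It is true that the definition is not written down. The harm does not follow. Early scans in a symmetric window are offset by late ones, which is why the even-spread figures stay near 5% and 84%. Section 14.0 attaches the 5% and 20% to its 6-month response rate, so only the conversion to weeks is open. Monthly visits, earlier imaging on suspicion of progression (Section 4.3) and institutional review of responses (Section 16.1.2, Response Review) limit what goes unseen. The all-treated denominator already keeps patients who progress, die or go unassessed out of the successes without removing them from the count.

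**Conclusion.** No change is called for. The gap is real but small, and the documents' own equation of 3 months, 3 cycles and 12 weeks fills it: the second scheduled scan, nominally week 24, decides. On that reading type I error is 5.1% and power 84% with scans over weeks 22 to 26, or 5.6% and 85% over weeks 20 to 28, in line with the stated 5% and 84%.

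This rests on scan times being spread roughly evenly around week 24 and on an assumed exponential failure curve; Weibull shapes 0.7 to 1.5 barely alter the week 22–26 type I error. Type I errors of 10% to 18% need calendar months or every scan at week 22, and 36% power needs a wait for week 36. The documents support none of these. The one substantive remedy, a window that opens only at week 24, would trade a design that already holds its errors for 3.4% and 80%, and would count slightly early scans as failures.

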11.1 TOXICITIES/SIDE EFFECTS

These adverse event management guidelines are intended to ensure the safety of each patient while attempting to characterize the safety and tolerability of the test products. In agreeing to the provisions of this protocol, the investigator accepts all legal responsibilities for prompt notification of SAEs to the SAE manager in the Office of Clinical Research and to AstraZeneca as per section 11.4.

Adverse events occurring during the study will be graded according to the NCI CTCAE Scale Version 3.0 (see http://ctep.cancer.gov/forms/CTCAEv3.pdf) where applicable. Adverse events that are not included on the toxicity scale will be designated as Grade 1 = mild, Grade 2 = moderate, Grade 3 = severe, Grade 4 = life-threatening, and Grade 5 = death.

The investigator should evaluate all adverse events and should make an immediate effort to determine their etiology. Adverse events that are determined not to be possibly, probably, or definitely related to study drug may not require further evaluation but will need to be recorded on the CRFs. Study medication may be interrupted for an adverse event at the discretion of the investigator. Patients requiring toxicity management should be assessed and evaluated at least weekly as indicated by the severity of the event.

11.2 Definitions

The definitions of adverse events (AEs) and serious adverse events (SAEs) are given below. It is of the utmost importance that all staff involved in the study is familiar with the content of this section. The principal investigator is responsible for ensuring this.

11.2.1 Adverse event

An adverse event is the development of an undesirable medical condition or the deterioration of a pre-existing medical condition following or during exposure to a pharmaceutical product, whether or not considered causally related to the product. An undesirable medical condition can be symptoms (*eg*, nausea, chest pain), signs (*eg*, tachycardia, enlarged liver) or the abnormal results of an investigation (*eg*, laboratory findings, electrocardiogram). In clinical studies, an AE can include an undesirable medical condition occurring at any time, including run-in or washout periods, even if no study treatment has been administered. In cancer clinical trials, many AEs are in fact related to progression of the patient's underlying malignancy.

An adverse event includes:

- An exacerbation of a pre-existing illness;
- An increase in frequency or intensity of a pre-existing episodic event or condition;
- A condition detected or diagnosed after study drug administration even though it may have been present prior to the start of the study;
- Continuously persistent disease or symptoms that were present at baseline and worsen following the start of the study.

IRB#: 07-022A(13)

An adverse event does not include:

- Medical or surgical procedures (eg, surgery, endoscopy, tooth extraction, or transfusion); however, the condition that leads to the procedure is an adverse event (Procedures that occur during the trial should be recorded on the Concurrent Procedure CRF);
- Pre-existing diseases, conditions or laboratory abnormalities present or detected at the start of the study that do not worsen;
- Hospitalizations or procedures that are done for elective purposes not related to an untoward medical occurrence (eg, hospitalizations for cosmetic or elective surgery or social/convenience admissions);
- The disease being studied or signs/symptoms associated with the disease unless more severe than expected for the patient's condition;
- Overdose of study drug without any clinical signs or symptoms.

